Subjects will be assigned post-injection blood draw at either 30 minutes, 45 minutes or 60 minutes after the gentamicin injection in a sequential fashion, meaning that participant #1 will have a 30 minute draw, #2 a 45 minute and #3 at 60 minute. This one green top tube of blood will be tested for gentamicin concentration as part of Objective 2 and Creatinine.

5. *Counseling:*

The study clinician will counsel the subject to avoid sexual activity, and most specifically performing oral sex, deep kissing, and oral-anal sex until they return for the TOC visit.

Test of Cure Visit

Subjects will return to the PHSKC STD Clinic to meet with the study clinician 4-7 days (+/- 1 day) after their enrollment visit. The study coordinator will call the subject the day prior to the visit as a reminder. At the TOC visit:

1. *Diagnostics:*

The study clinician will obtain a pharyngeal culture for *N. gonorrhoeae* and a blood draw for a follow-up creatinine. (Specimen processing per above). If the culture is positive for *N. gonorrhoeae*, the subject will be called to return for standard of care treatment – Ceftriaxone 250mg IM plus Azithromycin 1g orally once.

2. *Behavior and Symptom screen:*

The study clinician will administer a standardized symptom screening form (see Appendix F) to assess for gentamicin side effects and tolerability. The form will also ask about sexual activity, including kissing, in the time period between treatment and TOC.

Retention Plan

The study coordinator will attempt to schedule the TOC visit at 4 days after the enrollment visit so that if the subject fails to show to that visit, there are still opportunities to reschedule the TOC visit. Additionally, although the subject will be compensated for their time in the study, they will not receive compensation until they return for the TOC visit. This is an incentive for them to keep their follow-up visit.

Data Sources and Data Management

PHSKC STD Clinic Medical Record: We will use gonorrhea test results that occurred prior to enrollment visit from the STD clinic medical record for inclusion criteria. This data will be extracted by chart review during the enrollment visit using subject name and DOB as identifiers. The information will then be entered using a subject ID in the study database. We will also use demographic and sexual behavior data from the medical record.

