Neisseria Reference Laboratory: The NRL will provide the antimicrobial susceptibility data for the *N. gonorrhoeae* isolates recovered at both enrollment and TOC visit. The culture specimens are clinical specimens and full antimicrobial susceptibility testing (AST; this includes, beta-lactamase, penicillin, tetracycline, ciprofloxacin, cefixime, ceftriaxone, azithromycin and gentamicin) is done on all isolates. However, AST is not routinely reported to the clinic. Thus, in order to obtain this data, we will submit a list of names and MRN to [name], the Director of the NRL, to pull the data for us. All personal health information (PHI) will be transferred electronically using secure file transfer technology.

Data Entry Form: The study coordinator and study clinician will record key data points on a paper data entry form which will be transcribed into electronic data entry form in RedCap. Data to be collected will come from both the STD Clinic medical record and patient interview. Data points will include: date of visit, gender identity, sex assigned at birth, age, race, height, weight, site of infections pre-enrollment and type of test used to diagnosis; time of administration of gentamicin, time of gentamicin concentration blood draw; results of treatment visit testing (culture results at each site); date of TOC visit, symptoms since treatment; sexual activity since treatment (including kissing, oral-anal, oral-penile, anal-penile, penile-vaginal etc); anatomic sites tested by culture and results; repeat treatment needed etc (see Appendices E and F)

UW Lab Medicine Research Testing Services: RTS will test our blood specimens for pre- and post- treatment Creatinine and gentamicin levels. We will give the specimens to them with study id's and dates on them, and they will provide the data via an excel file with only study ID and results.

Data Management

We will use RedCap to collect and store all study data. Data can be exported from RedCap as a Stata database, which will be used for analysis. Upon export from RedCap, we will remove identifiers except for subject ID and maintain a separate database to link subject identifiers/contact info to subject ID.

Study Confidentiality and Security

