- 2) Evaluate the renal safety and tolerability of 360mg IM of gentamicin.
- 3) Document mean peak gentamicin levels following 360mg IM of gentamicin stratified by weight.
- 4) Estimate the best pharmacodynamics criterion (i.e. peak/MIC ratio) for pharyngeal gonorrhea treated with gentamicin *using individual* and mean peak gentamicin levels and NG isolate MIC.
- 5) Among treatment failures, *conduct exploratory analyses* comparing pre- and post-treatment MIC for evidence of induced resistance.

Analyses

The primary endpoint is the pharyngeal cure rate – that is, the proportion of subjects who return for TOC who clear their infections as evidenced by a negative culture 4-7 (+/-1) days after treatment. The cure rate will be calculated as the number of cured subjects divided by the total number of subjects who received treatment and returned for follow-up testing in a modified an intention to treat (mITT) analysis. We will also calculate the 95% CI for this proportion.

$$\text{Cure rate} = \frac{\text{number of subjects with negative pharyngeal culture at TOC}}{\text{number of subjects with + throat test at enrollment \& received gentamicin}}$$

Persons who test negative for NG at their enrollment visit (i.e. infection cleared between initial clinical screening test and enrollment) will be excluded from analysis. Treatment failure will be defined as a positive culture 4-7 (+/-1) days after treatment.

For our second objective, we will obtain pre- and post-treatment serum creatinine. An elevation of >40% will be considered significant. We will evaluate subject's tolerability (Obj. 2) using a standardized symptom questionnaire (see Appendix F) conducted at the TOC visit. The symptoms questioned will include, but not be limited to, rash, tinnitus, decreased hearing, nausea, vomiting, diarrhea, headaches, and decreased appetite. There will also be a section for free response.

Our third objective is to document the pharmacokinetics of 360mg of IM gentamicin by weight. We will obtain serum gentamicin levels at 30, 45 and 60minutes post dosing based on previous studies that estimated that IM gentamicin peaks between 30-60 minutes post-dose.

We will stratify the results by time post-dose, as well as by subject weight in kilograms (categorized).

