In order to estimate the ideal PK/PD criterion, we will compare the MIC of cures to treatment failures using a stratified approach (Table 2), and we will correlate this data with individual peak gentamicin level in order to estimate the ideal pharmacodynamic (PD) criterion (Obj. 4). As these results are ratios and may have a skewed distribution, we will log transform them and calculate a geometric mean. We anticipate that the vast majority of isolates will have a gentamicin MIC ≤ 8 $\mu\text{g/mL}$, and that most subjects' peak concentration will be between 16-27 $\mu\text{g/mL}$ giving a ratio of 2-4. Variations in subjects' weight or the gentamicin MICs might alter those predictions. Assuming an 80% cure rate ($n=40$), and a mean ratio of 3, with a standard deviation of 1, we anticipate a 95% CI of the peak/MIC ratio of 2.7 – 3.3, suggesting that our sample size is adequate to calculate this ratio.

For persons who fail treatment we will also compare the pre- and post-treatment gentamicin MIC to estimate whether single dose gentamicin therapy can “induce” resistance (Obj. 5) in an exploratory analysis. We will consider an increase in the MIC by two doubling-dilutions (i.e. from MIC of 2 to 8 $\mu\text{g/mL}$, or 8 to 32 $\mu\text{g/mL}$) to represent induced resistance, and we will calculate the proportion of isolates among those that fail treatment that demonstrate induced resistance following receipt of gentamicin. Should we see a signal for induced resistance, we plan to apply for additional funding to conduct whole genome sequencing to look for genetic determinants of resistance.

Table 2: Proposed Description of Primary Study Findings

GENTAMICIN MIC ($\mu\text{g/mL}$)	Cure (N=XX)	Treatment Failures (N=XX)	Gentamicin Serum Level (Mean, Range)	Peak/MIC Ratio (Mean, Range)
≤ 1				
2				
4				
8				
16				
32				
≥ 64				

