APPENDIX F

Study ID: _____

The Gent Study – TOC Visit Data Entry Form

TOC Visit Date: _____ Days since Tx: _____

Symptoms since Tx:

Y or N Headache (if yes, characterize): _____

Y or N Vision Changes (if yes, characterize): _____

Y or N Changes in Hearing (if yes, characterize): _____

Y or N Tinnitus (if yes, characterize): _____

Y or N Urinary Symptoms (if yes, characterize): _____

Y or N Nausea or Vomiting (if yes, characterize): _____

Y or N Diarrhea (if yes, characterize): _____

Y or N Constipation (if yes, characterize): _____

Y or N Rash (if yes, characterize): _____

Y or N Other (if yes, characterize): _____

Sexual Activity Since Treatment:

1) Have you been intimate with any partners since treatment? Y or N
(*Intimacy includes kissing, oral-anal sex, oral-penile sex, anal-penile sex, penile-vaginal sex*)

2) Were any of your partners since treatment the same as someone you were intimate with in the 2 months prior to your pharyngeal gonorrhea diagnosis? Y or N

If Yes to #1 above, ask the following questions:

3) How many days did you deep kiss a partner since treatment? _____

4) How many partners did you deep kiss since treatment? _____

5) How many times did you perform oral sex on a penis since treatment? _____

- 6) How many male-bodied persons did you give oral sex to since treatment? _____
- 7) How many times did you rim a partner since treatment? _____
- 8) How many partners did you rim since treatment? _____
- 9) How many times did you top (i.e. insertive anal intercourse) a partner since treatment?

- 10) How many partners did you top since treatment? _____
- 11) How many times did you bottom (i.e. have receptive anal intercourse) for a partner since treatment? _____
- 12) For how many partners did you bottom since treatment? _____
- 13) How many times did you have vaginal sex with a partner since treatment? _____
- 14) How many partners did you have vaginal sex with since treatment? _____

TOC Testing Conducted and Results:

Pharynx: NAAT Result Positive Negative

Culture Done Yes No

Culture Results Positive Negative

AST results (in mcg/mL): PCN: _____ TET: _____ CIP: _____

CFX: _____ CTX: _____ AZM: _____ GENT: _____

Rectum: NAAT Result Positive Negative

Culture Done Yes No

Culture Results Positive Negative

AST results (in mcg/mL): PCN: _____ TET: _____ CIP: _____

CFX: _____ CTX: _____ AZM: _____ GENT: _____

Urethra: NAAT Result Positive Negative

Culture Done Yes No

Culture Results Positive Negative

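### The exploratory induced-resistance outcome does not check that the enrolment and test-of-cure isolates are the same strain, so a higher-MIC strain acquired after treatment would count as a gentamicin effect

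*Combined protocol and SAP*

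**What the plan says.** The rule appears twice: in the Statistical Analysis Plan of the opening summary, where it is labelled objective 3, and in the Data Analysis section, where it is objective 5. Both use the sentence "We will consider an increase in the MIC by two doubling-dilutions", give 2 to 8 and 8 to 32 µg/mL as examples, and treat such a rise as induced resistance. The reported quantity is the "proportion of isolates among those that fail treatment that demonstrate induced resistance following receipt of gentamicin".

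The denominator is defined by culture alone: "Treatment failure will be defined as a positive culture 4-7 (+/-1) days after treatment". Reinfection is not separated from persistence.

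Three other parts of the protocol bear on whether the isolates match:

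- **Susceptibility data.** Under Data Sources, "The NRL will provide the antimicrobial susceptibility data for the *N. gonorrhoeae* isolates recovered at both enrollment and TOC visit". The panel covers beta-lactamase, penicillin, tetracycline and ciprofloxacin as well as "cefixime, ceftriaxone, azithromycin and gentamicin) is done on all isolates".
- **Re-exposure.** Under Test of Cure Visit, "The form will also ask about sexual activity, including kissing, in the time period between treatment and TOC". Appendix F asks "Have you been intimate with any partners since treatment", and whether any of those partners date from before the diagnosis.
- **Sequencing.** If a signal for induced resistance is seen, "we plan to apply for additional funding to conduct whole genome sequencing to look for genetic determinants of resistance".

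None of these enters the definition of induced resistance, and no analysis of the exposure answers is described.

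**The concern.** The outcome is named for a cause, but only a difference between two cultures is measured. That difference can arise in at least two ways: the original strain's MIC rose under gentamicin, or the subject cleared the original strain and acquired another with a higher MIC before the TOC visit. The rule gives both the same label.

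The sequencing step does not close the gap. It depends on a signal having appeared and on new money, and its stated purpose is to find resistance determinants, not to confirm that the paired isolates match. The proportion would be reported in any case.

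At stake is how a small exploratory result is read. With so few failures expected, one wrongly labelled pair could be the whole signal, and could prompt the funding application.

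**Working it through.** The documents give no sample size, power or error rate for this objective, so there is no planned figure to reproduce.

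**1. The threshold.** Two doubling dilutions are 2² = 4-fold. The plan's examples agree: 8/2 = 4 and 32/8 = 4.

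**2. Expected failures.** The Data Analysis section pairs an 80% cure rate with n = 40. Read as 40 cures, that implies 40/0.80 = 50 evaluable subjects and 50 − 40 = 10 failures. If all 60 planned subjects were evaluable, failures would be 60 × 0.20 = 12.

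**3. Weight of one pair.** The shift is 100/f percentage points for f failures.

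- f = 10: 10 points. A result of 1/10 has an exact (Clopper-Pearson) 95% CI of 0.3% to 44.5%.
- f = 12: 8.3 points. A result of 1/12 has an exact 95% CI of 0.2% to 38.5%.

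These sizes apply only once a pair has been misclassified.

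**4. How often this could happen (illustration only).** A false label needs two things: the TOC isolate is a new strain (probability r per failure), and its MIC is at least 4-fold above the old one (probability q, given a new strain). The chance of at least one false label is P = 1 − (1 − rq)^f. The documents give neither r nor q, so all values below are assumptions. For q, the old and new strains are taken as independent draws from one MIC distribution:

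- Narrow: MIC 4 and 8, half each. No pair differs 4-fold, so q = 0.
- Middle: MIC 2, 4, 8, 16 at 10%, 40%, 45%, 5%. q = 0.10 × 0.50 + 0.40 × 0.05 = 0.07.
- Wide: MIC 1, 2, 4, 8, 16 at 10%, 25%, 30%, 25%, 10%. q = 0.10 × 0.65 + 0.25 × 0.35 + 0.30 × 0.10 = 0.1825.

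For example, r = 0.10, q = 0.07 and f = 10 give 1 − 0.993^10 = 6.8%.

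| r | q = 0 | q = 0.07 (f = 10 / 12) | q = 0.1825 (f = 10 / 12) |
|---|---|---|---|
| 5% | 0% | 3.4% / 4.1% | 8.8% / 10.4% |
| 10% | 0% | 6.8% / 8.1% | 16.8% / 19.8% |
| 20% | 0% | 13.2% / 15.6% | 31.1% / 36.0% |
| 30% | 0% | 19.1% / 22.5% | 43.1% / 49.1% |

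The spread from 0% to 49% shows that the answer depends on the assumptions. It is not an estimate for this trial.

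**The case against.** The sponsor has a fair reply, in four parts.

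- **Status.** The analysis is labelled exploratory, the plan says only that it will attempt to determine the effect, and the verb is placed in inverted commas. No stopping rule, sample size or primary conclusion rests on it. This stands and keeps the point minor. It does not make the label accurate, because the definition still says that such a rise represents induced resistance.
- **Mitigation.** Subjects are counselled to avoid sexual activity, particularly oral sex, deep kissing and oral-anal sex, until TOC, and the interval is only 4 to 7 days, plus or minus one. This lowers the chance of a new strain. It does not remove it, and neither measure is a condition of the analysis.
- **Frequency.** A reader might infer that false signals are likely: if 10% of failures were new strains, the chance of at least one among 10 is 1 − 0.90^10 = 65%, and at 5% it is 1 − 0.95^10 = 40%. Those are chances of a new strain being present, not of a false label, which also needs a 4-fold higher MIC. The plan expects the vast majority of MICs at or below 8 µg/mL, which narrows the room for such a rise but does not exclude it (2 to 8 qualifies). With the assumed q values, and 10 failures, the figures fall to 0% to 17% and 0% to 9%.
- **Remedy.** Agreement in susceptibility profile can flag a different strain but cannot prove the same one: a new strain with a common profile would pass. Nor would any matching separate induction from selection within a mixed baseline infection. Both limits stand and shape the fix.

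**Conclusion.** The gap is real and minor. As written, both statements of the rule would count a higher-MIC strain acquired after treatment as resistance caused by gentamicin, and nothing elsewhere in the protocol prevents this.

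The size that can be relied on is conditional: each misclassified pair moves the proportion by 8 to 10 percentage points. This rests on the 80% cure-rate hypothesis and on 50 to 60 evaluable subjects; with a lower cure rate there would be more failures and each pair would weigh less. The event should be uncommon, and its probability cannot be derived from the documents.

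A reader might infer that the trial sets out to make a firm causal claim, or that its induced-resistance result will probably be wrong. The documents support neither: the aim is exploratory and hedged, and the frequency of new strains is unknown. What they support is that the outcome's name claims more than its definition can show.

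**What to change.** In both places where the rule appears:

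1. Name the outcome *MIC increase of at least two doubling dilutions in the TOC isolate*, and report that proportion among treatment failures.
2. Report as *possible induced resistance* only those pairs whose beta-lactamase result and six other MICs (penicillin, tetracycline, ciprofloxacin, cefixime, ceftriaxone, azithromycin) show no evidence of a different strain. Fix the concordance tolerance in advance with the reference laboratory.
3. List discordant pairs separately as possible new strains, with their Appendix F exposure answers.
4. State that agreement in susceptibility profile does not prove strain identity.

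No new specimen or assay is needed, since the panel is already run on all isolates and the exposure questions are already asked. Fixing the rule before results are seen matters because reclassifying pairs afterwards, among about 10, would be hard to defend.

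There are two costs. Some true cases may be set aside as unclassified, although they remain in the first proportion and in the listing. The susceptibility results must also be captured for both isolates: the enrolment form (Appendix E) has no susceptibility fields and the TOC form (Appendix F) has none for beta-lactamase, so the forms or the laboratory data transfer need a small addition.

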The proposed study aims to evaluate the efficacy of a single intramuscular (IM) dose of gentamicin in the treatment of pharyngeal gonorrhea. Secondary objectives include documenting the efficacy stratified by minimal inhibitory concentration (MIC) compared with the gentamicin peak level in order to estimate a pharmacodynamic criterion. We will also attempt to determine whether gentamicin monotherapy induces antimicrobial resistance among treatment failures. Lastly, we will evaluate the tolerability of 360 mg of IM gentamicin, stratified by subject weight (i.e. weight based dosing). The specific aims are:

- 1) Determine the proportion of persons whose pharyngeal gonococcal infections are cured with a single dose of 360mg gentamicin intramuscularly alone.
- 2) Evaluate the *renal safety* and tolerability of 360mg IM of gentamicin.
- 3) Document mean peak gentamicin levels following 360mg IM of gentamicin stratified by weight.
- 4) Estimate the best pharmacodynamics criterion (i.e. peak/MIC ratio) for pharyngeal gonorrhea treated with gentamicin using individual and mean peak gentamicin levels and NG isolate MIC.
- 5) Among treatment failures, conduct exploratory analyses comparing pre- and post-treatment MIC for evidence of induced resistance.

Study Design: Prospective cohort

Study Population & Inclusion Criteria:

Persons diagnosed with pharyngeal gonorrhea who are not yet treated

Exclusion criteria:

- Age less than 16 years
- Receipt of antibiotics in ≤ 30 days
- Known allergy to any aminoglycoside
- History of renal disease (including diagnosis of solitary kidney, chronic renal insufficiency, renal cell carcinoma etc),
- Use of concurrent nephrotoxic drugs or muscle relaxants
- History of diabetes
- History of hearing loss or tinnitus
- Concurrent infection with syphilis or chlamydia
- Pregnancy and/or nursing
- Unable to return for a follow-up visit 4-7 days (+/- 1 day).
- Study team's discretion

Intervention: 360mg IM gentamicin x 1

Primary Outcome: Negative gonorrhea culture 4-7 days (+/- 1 day) after treatment

Sample Size: 60 persons

Statistical Analysis Plan:

[figure not shown]

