The primary endpoint is the pharyngeal cure rate – that is, the proportion of subjects who return for TOC who clear their infections as evidenced by a negative culture 4-7 (+/-1) days after treatment. Persons who test negative for NG at their enrollment visit (i.e. infection cleared between initial clinical screening test and enrollment) will be excluded from analysis. Treatment failure will be defined as a positive culture 4-7 (+/-1) days after treatment. The cure rate will be calculated as the number of cured subjects divided by the total number of subjects who received treatment and returned for follow-up testing in a modified an intention to treat (mITT) analysis. We will also calculate the 95% CI for this proportion.

We will conduct an interim analysis after we have primary outcome results for 25 subjects. If the cure rate is $\leq 44\%$ (99% CI 17% – 74%; i.e. 12 persons of 25 persons with a positive culture on treatment date fail treatment), we will stop the study. We will also monitor for renal toxicity at the interim analysis. We plan to obtain pre-treatment and post-treatment Creatinine. Increases $>40\%$ will be considered significant. If more than 20% of the study population has a $>40\%$ increase in serum Creatinine, we will halt the study. We chose 20% because if 20% of subjects experience renal toxicity it is unlikely to be due to chance (95% CI 7 – 40%). For our second objective, we will compare the MIC of cures to treatment failures using a stratified approach (Table 2), and we will correlate this data with individual peak gentamicin level in order to estimate the ideal pharmacodynamic (PD) criterion (Obj. 2). For persons who fail treatment we will also compare the pre- and post-treatment genatmicin MIC to estimate whether single dose gentamicin therapy can “induce” resistance (Obj. 3) as an exploratory analysis. We will consider an increase in the MIC by two doubling-dilutions (i.e. from MIC of 2 to 8 $\mu\text{g/mL}$, or 8 to 32 $\mu\text{g/mL}$) to represent induced resistance, and we will calculate the

proportion of isolates among those that fail treatment that demonstrate induced resistance following receipt of gentamicin. Lastly, we will report the number and proportion of subjects who report side effects.

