The NRL first determines cefixime, ceftriaxone and azithromycin MIC by the etest method initially for prompt clinical action. Then, gonorrhea isolates undergo AST according to the Clinical and Laboratory Standards Institute (CLSI) recommended agar dilution method for further surveillance.[13] AST testing includes: Penicillin (PEN), Tetracycline (TET), Cefixime (CFM), Ceftriaxone (CRO), Ciprofloxacin (CIP), Azithromycin (AZM), and Gentamicin (GEN). We used CLSI[15] breakpoints to interpret MICs for penicillin ($\geq 2.0\mu\text{g/ml}$), tetracycline ($\geq 2.0\mu\text{g/ml}$), spectinomycin ($\geq 128.0\mu\text{g/ml}$), and ciprofloxacin ($\geq 1.0\mu\text{g/ml}$),[15] and used GISP alert values for azithromycin ($\geq 2.0\mu\text{g/ml}$), cefixime ($\geq 0.25\mu\text{g/ml}$), and ceftriaxone ($\geq 0.125\mu\text{g/ml}$) as CLSI has not established breakpoints for these antimicrobial agents.[12] Neither CLSI nor CDC have published breakpoints for gentamicin however, other institutes have used the following breakpoints that we will follow in this study: Resistant is $\geq 32\mu\text{g/ml}$; Intermediate susceptible 8-16 $\mu\text{g/ml}$, and Susceptible $\leq 4\mu\text{g/ml}$. Full AST results will be reported to the PI.

Data Safety and Monitoring Plan, Resolving & reporting Protocol Deviations, AEs and Unanticipated problems

OVERSIGHT RESPONSIBILITIES

Day-to-day oversight of the trial is provided by the Principal Investigator (PI), [name], along with [name] (co-I). [name] assures that informed consent is obtained prior to performing any research procedures, that all subjects meet eligibility criteria, and that the study is conducted according to the IRB-approved research plan. Drs. [name] and [name] review all study data and any adverse events (AEs) real-time, and report all SAEs to the Medical Monitor and IRB according to the approved DSMP.

Medical Monitor: Monitoring for the study will be provided by a volunteer Medical Monitor, [name], Professor of Medicine in the Division of Allergy and Infectious Diseases, who has over 25 years of experience with clinical trials, but is not directly related to the study team.

MONITORING PROCEDURES

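### The exploratory resistance summary counts only MIC rises of two dilutions and calls each one induced, so with 8 to 12 failure pairs and no untreated comparison it cannot separate residual assay variation from a drug effect

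*Combined protocol and SAP*

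**What the plan says.** The last specific aim, listed under Objectives and again under Data Analysis, is to "conduct exploratory analyses comparing pre- and post-treatment MIC for evidence of induced resistance" among treatment failures. The method appears in the Statistical Analysis Plan section near the front (as Obj. 3) and again under Data Analysis, Analyses (as Obj. 5):

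- The comparison is paired: "For persons who fail treatment we will also compare the pre- and post-treatment gentamicin MIC".
- The criterion is one-directional: "We will consider an increase in the MIC by two doubling-dilutions" to represent induced resistance. The examples are 2 to 8 and 8 to 32 μg/mL.
- The summary is a single proportion: "we will calculate the proportion of isolates among those that fail treatment that demonstrate induced resistance following receipt of gentamicin".
- Data Analysis adds a consequence: "Should we see a signal for induced resistance, we plan to apply for additional funding to conduct whole genome sequencing", to look for genetic determinants. The size of a signal is not defined.

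On the assay, Laboratory Processing says that "gonorrhea isolates undergo AST according to the Clinical and Laboratory Standards Institute (CLSI) recommended agar dilution method for further surveillance". It states no repeatability figure, no replicate reading and no testing of the two isolates of a pair in one run. Data Sources and Data Management confirms that gentamicin susceptibility results come from isolates at both enrollment and test of cure. The design is a prospective cohort with one treatment.

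**The concern.** Two readings of the same strain, with the same true MIC, can differ. If reading error is symmetric, a fall of two dilutions is as likely as a rise of two. A proportion that counts only rises cannot go below zero, so any such error can only push it up. No untreated group shows how often rises occur without the drug, and the paired falls that could indicate the size of the noise are not tabulated.

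The denominator is small. One rise among 8 to 12 failures would be reported as 8–13% induced resistance (1/12 to 1/8). The label asserts a cause that the statistic cannot establish. One such pair could also count as the undefined signal that leads to a sequencing application.

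**Working it through.** The plan gives no expected proportion, power or interval for this objective, so there is no figure to reproduce. Both of its examples fit its rule: log2(8/2) = 2 and log2(32/8) = 2.

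**Number of failure pairs.** The inputs are "Sample Size: 60 persons" and, from Data Analysis, "Assuming an 80% cure rate ($n=40$), and a mean ratio of 3, with a standard deviation of 1".
- If 40 is the number evaluable: 40 × 0.20 = 8 failures.
- If 40 is the number of cures: 40/0.80 = 50 evaluable, so 10 failures.
- If all 60 are evaluable: 60 × 0.20 = 12 failures.

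**False rises with no true change.** Assay error is an assumption, so two models were run over a range.

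*Model A.* Each reading is independently one dilution high with probability q, one low with probability q, and otherwise correct. A two-dilution rise needs the first reading low and the second high, so P(rise ≥ 2) = q². A two-dilution fall has the same probability. A rise of one step or more has probability q² + 2q(1 − 2q).

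P(at least one false rise in m pairs) = 1 − (1 − q²)^m:

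| q | P(rise ≥ 2) per pair | m = 8 | m = 10 | m = 12 |
|---|---|---|---|---|
| 0.05 | 0.25% | 2.0% | 2.5% | 3.0% |
| 0.10 | 1.0% | 7.7% | 9.6% | 11.4% |
| 0.20 | 4.0% | 27.9% | 33.5% | 38.7% |
| 0.25 | 6.25% | 40.3% | 47.6% | 53.9% |

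*Model B.* Normal error on the log2 scale around a true MIC placed uniformly within a dilution step, with each reading rounded up to the next dilution:

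| SD (log2) | P(rise ≥ 2) per pair | m = 10 |
|---|---|---|
| 0.3 | 0.13% | 1.3% |
| 0.5 | 2.5% | 22% |
| 0.7 | 7.3% | 53% |

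Falls of two or more dilutions are equally likely under this model too.

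**What the threshold removes.** At q = 0.10, a chance rise of one step or more has probability 0.01 + 2 × 0.10 × 0.80 = 17% per pair. A rise of two or more has probability 1%.

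**Expected false rises in 10 pairs.** 10 × 0.0025 = 0.025 at q = 0.05, and 10 × 0.0625 = 0.625 at q = 0.25.

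**What one rise shows.** 1/10 has an exact 95% interval of 0.3% to 44.5%. In a sign test, one rise and no falls gives a one-sided p of 0.5. Five rises with no falls are needed for one-sided p < 0.05 (0.5⁵ = 0.031), and six for two-sided (2 × 0.5⁶ = 0.031).

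**Would 'more rises than falls' serve as the sequencing trigger?** Under Model A with 10 pairs and no true change, that rule is met in 8.8% of trials at q = 0.10, against 9.6% for any rise. At q = 0.20 the figures are 24.5% and 33.5%. It leaves most of the false-trigger rate in place.

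**The case against.** The strongest reply is that the plan already guards against ordinary reading variation. It requires a fourfold change, and under Model A a false one needs both readings to err, in opposite directions. With a tight assay, 97% or more of null trials with 10 failures would report no rise at all. This stands. A reader might infer that routine one-step variation is being reported as a drug effect. The documents do not support that, because one-step differences are not counted. Only residual variation of two or more dilutions is at issue, and its frequency rests on a repeatability figure that the documents do not give.

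The second reply is that little hangs on the result. The text repeatedly calls the analysis exploratory, and the only consequence is a funding application for sequencing, which would itself look for a genetic basis. This also stands, and it sets the priority. A reader might infer that a false signal would compromise the trial's conclusions. It would not: the cure rate and the stopping rules do not use this proportion.

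Third, the plan commits to comparing pre- and post-treatment MIC before it names the proportion, so falls are not excluded. True, but nothing commits the report to showing them.

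Fourth, falls are not a pure noise control. A different strain at the test of cure could move the MIC either way. Appendix F records sexual activity since treatment, but the analysis does not say how that will be used. This stands, so falls are a useful reference and not a clean correction.

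**Conclusion.** The point holds in a limited form. The planned summary counts one direction of change, attaches a causal label, has no interval and has no untreated comparison. With about 8 to 12 pairs it cannot tell residual assay variation of two or more dilutions from a drug effect. For 10 pairs with no true change, the chance of at least one false rise is about 1–3% if the assay is tight (q = 0.05 or SD 0.3) and about 50% if it is loose (q = 0.25 or SD 0.7).

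These figures assume independent, symmetric reading errors and an 80% cure rate. The error sizes are assumptions and not properties of the laboratory's assay. A false signal is therefore possible, but it is not the expected result unless the assay is imprecise. Priority is low.

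**What to change.** In the Statistical Analysis Plan section and under Data Analysis, replace the rises-only proportion with:

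- the full distribution of paired log2 MIC change among failures;
- the numbers of pairs with a rise, and with a fall, of two or more dilutions, side by side;
- the proportion with such a rise and its exact 95% interval;
- a signed-rank or sign test of the paired change, labelled descriptive, since it has little power at this size.

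Call an individual rise an MIC increase and not induced resistance. Do not make an excess of rises over falls the trigger for sequencing, since one rise with no falls would meet it. State that showing falls does not rule out reinfection with another strain.

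The cost is a change of wording, a slightly larger table and a less definite statement about induction. No new data are needed, because isolates from both visits already receive gentamicin susceptibility testing.
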